 - Approximately 25% of each type of challenge (meal or exercise) will be performed on 3 consecutive days within each of the following 4 periods time from randomization: 1-2 weeks, 3-4 weeks, 5-6 weeks, 7-8 weeks. Challenges that cannot be scheduled during these time periods or challenges that need to be rescheduled may be performed, if necessary between weeks 9 and 13.

Chapter 1: Background Information

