4.6 Instructions for the AID Group

The approach to training will depend on whether the participant is already a pump user. The training on use of the AID system may occur completely at this visit or may be spread out over a few days in multiple visits or contacts. Initiation of the study pump and closed-loop control generally will occur on the day of the Randomization Visit but can be deferred if the investigator believes additional training is needed prior to initiating the study pump. In such cases, initiation of the study pump and Control IQ should occur no more than 7 days following randomization.

Participants will be informed of the need to have a care partner trained and capable of treating severe hypoglycemia, including use of glucagon as indicated in section 6.3.

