# 2. Comparison with the Protocol

The author of this document confirms that this SAP is consistent with version 5.0 of the Protocol, exceptthe following:

- New formal analyses were added to compare the night following meal or exercise challenges with the previous 14 nights without any previous day challenge.
- 94 95

96 97

101

103 104

92

93

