- Thirteen Weeks of Follow-up: All CGM data following the randomization will be included. 223 • Since the meal and exercise sessions are designed as challenges to the system and the data to be 224 analyzed for possibly induced safety events, the CGM data between the start of the meal or 225 exercise and 6:00AM next morning will be analyzed separately (see Sections 5.4 and 5.5 below) 226 and not included here. If the 13-week visit is more than 13 weeks after the randomization visit 227 for a participant, then the CGM data will be truncated at 13 weeks (i.e., 91 days). At least 168hr 228 229 of data during these 13 weeks of follow-up are required for the glycemic metrics to be calculated 230 and for a participant to be included in the glycemic analyses. These are either Tandem pump CGM data or Dexcom CGM data if obtained to fill any Tandem data gaps. 231
- All CGM metrics during baseline and follow-up periods will be calculated giving equal weight to
   each sensor reading for each participant.
- Calculation of CGM metrics for the treatment group comparisons will exclude the challenges and the period through 6AM on the day following the end of the challenge. CGM metrics during and following the challenges will be reported separately as described in Sections 5.4. and 5.5; while an overall analysis will be performed for all CGM data in the AID group (i.e., including the challenge data) as described in Section 17.
- CGM-measured prolonged hyperglycemia events are defined as ≥90 cumulative minutes with CGM glucose >300 mg/dL within a 120-minute period (the participant becomes eligible for another prolonged hyperglycemia event after the CGM glucose is <180 mg/dL for ≥15

   consecutive minutes).
- CGM-measured hypoglycemia events are defined as ≥15 consecutive minutes with CGM glucose <54 mg/dL (the participant becomes eligible for another hypoglycemia event after the CGM glucose is ≥70 mg/dL for ≥15 consecutive minutes). For each of these metrics, the number of events per week is calculated for each participant and each metric is then analyzed as a continuous variable as described below.

- 248 249

257

258

259

260

261

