### 250 **5.4 Calculation of CGM Metrics for Meal Challenges**

- The meal challenges will happen and the metrics will be calculated only during the 13 weeks of
   follow-up in the AID group, and are based on either Tandem pump CGM data or Dexcom CGM
   data if obtained to fill any Tandem data gaps.
- Will be calculated only if the meal challenge session was recorded on the CRF. The date-time of
   the challenge-related events, along with other relevant details about the challenge will be
   recorded on the CRF and will be tabulated.
  - All data between the start of the meal challenge and 6:00AM next morning will be included.
  - For each meal, two different periods will be considered, and two separate glycemic metrics will be calculated:
  - During and two hours following the end of the meal the period between the start and 4 hours following the end of meal as recorded on CRF, and
- 262 > Overnight following the meal the period between 4 hours following the end of the meal and 6:00AM next morning.

- At least 2hr (or 24 CGM readings) are required for each one of the two periods associated with an individual meal session for the CGM metrics to be calculated.
  - Each CGM reading during a meal session will be given equal weight.
- The unit of analysis is an individual meal challenge session and any participant with at least one meal challenge completed will be included in these analyses.
  - The metrics calculated and reported here will include % time below 54, 70, 70-180, above 180, 250, 300 mg/dL and mean glucose.
- The above glycemic metrics will be calculated during the night following the meal challenge (10PM to 6AM) and will be compared with the corresponding metrics calculated during 14 nights without any challenge in the previous two days. Nights prior to the challenge will be used if available, then nights subsequent to the challenge if needed to obtain 14 total nights. The nights will be pooled together when compared with the night following the meal challenge. At least 6hr of CGM data are required for the night following the meal challenge and at least 72hr are required for the pooled 14 nights for these metrics to be calculated and formally compared.

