#### 279 5.5 Calculation of CGM Metrics during Scheduled Exercise Challenges

- The exercise challenges will happen and the metrics will be calculated only during the 13 weeks
   of follow-up in the AID group, and are based on either Tandem pump CGM data or Dexcom
   CGM data if obtained to fill any Tandem data gaps.
  - Will be calculated only if the exercise session was recorded on the CRF. The date-times of the challenge-related events, along with other relevant details about the challenge will be recorded on the CRF and will be tabulated.
  - All data between the start of the exercise challenge and 6:00AM next morning will be included.
    - For each exercise, two different periods will be considered, and two separate glycemic metrics will be calculated:
      - During and two hours following the end of the exercise the period between the start and 2 hours following the end of exercise as recorded on CRF, and
      - Overnight following the exercise the period between 2 hours following the end of the exercise and 6:00AM next morning.
- At least 1hr (or 12 CGM readings) are required for each one of the two periods associated with an individual exercise session for the CGM metrics to be calculated.
  - Each CGM reading during an exercise session will be given equal weight.
    - The unit of analysis is an individual exercise session and any participant with at least one exercise challenge completed will be included in these analyses.
- The metrics calculated and reported here will include % time below 54, 70, 70-180, above 180, 250, 300 mg/dL and mean glucose.
- The above glycemic metrics will be calculated during the night following the exercise challenge (10PM to 6AM) and will be compared with the corresponding metrics calculated during 14 nights without any challenge in the previous two days as described above for meal challenges.
   The nights will be pooled together when compared with the night following the exercise challenge. At least 6hr of CGM data are required for the night following the exercise challenge and at least 72hr are required for the previous and pooled 14 nights for these metrics to be calculated and formally compared.
- 307

266

269

270

278

283

284

285 286

287

288

289

290

291

292

295

296

297

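### The 14 reference nights for the challenge comparison need not be nights on the AID system, so pre-AID nights enter for deferred starters with early challenges

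*SAP*

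**What the plan says.** SAP 5.4 takes the CGM metrics for 10PM to 6AM after a meal challenge and compares them with the same metrics pooled over 14 nights that had no challenge in the two preceding days. The order of selection is "Nights prior to the challenge will be used if available, then nights subsequent to the challenge if needed to obtain 14 total nights". SAP 5.5 uses "14 nights without any challenge in the previous two days as described above for meal challenges" for exercise. SAP 8.3 makes this a formal comparison with a mixed linear model and refers back to 5.4 for how the 14 nights are obtained.

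Two provisions set the time limits of the pool:
- The first bullet of 5.4 reads "The meal challenges will happen and the metrics will be calculated only during the 13 weeks of" follow-up, in the AID group. The first bullet of 5.5 has the same limit: "The exercise challenges will happen and the metrics will be calculated only during the 13 weeks".
- SAP 5.3 starts follow-up at randomization: "All CGM data following the randomization will be included". Baseline CGM is defined there as a separate period.

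Pump start can come later than randomization. Protocol 4.6 says "initiation of the study pump and Control IQ should occur no more than 7 days following randomization", while the footnote on the Randomization Visit in Protocol Table 1 (repeated in SAP Table 2) allows 14 days. Challenges are timed from randomization, with about a quarter of each type "within each of the following 4 periods time from randomization: 1-2 weeks, 3-4 weeks, 5-6 weeks, 7-8 weeks" (Protocol synopsis and Table 1, footnote k).

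SAP 2 summarizes the same analysis differently, as a comparison "with the previous 14 nights without any previous day challenge".

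**The concern.** The challenges are performed on the AID system, and the comparison asks whether a reduced or omitted bolus, or exercise, makes the following night worse. That question needs reference nights on the same system. As written, a night qualifies if it falls after randomization, has CGM data and is clear of challenges. A night after randomization but before pump start meets all three conditions and, because prior nights are taken first, is chosen ahead of later AID nights.

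The same gap exists at the other end. Protocol 5.5 asks participants who stop the AID system to keep wearing the study CGM to week 13. An early challenge needs subsequent nights to reach 14, and nothing prevents those from falling after discontinuation.

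If glucose is higher off the system, the reference looks worse than ordinary AID nights and a real post-challenge rise is understated. This is the only formal challenge comparison in the SAP, and SAP 5.3 says the challenge data are to be examined for induced safety events.

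**Working it through.** The documents give no size or power for this comparison, so there is no stated figure to reproduce. The check is a count of which nights the rule selects.

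**Conventions.** Day 0 is randomization, and night *t* begins on the evening of day *t*. AID starts on day *s*. A block of three consecutive challenge days starts on day *d* ≥ *s*. A night is eligible if no challenge fell on that day or the day before. The pool runs from day 0 to day 90. Prior nights are taken first, nearest to the block, then subsequent nights up to 14. One block is modeled; a second block of the other challenge type would push the look-back some nights earlier.

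**Count of pre-AID nights among the 14.**
- For *d* ≤ 14, all *d* prior nights are used, so the pre-AID count is *s*.
- For *d* > 14, the look-back covers nights *d* − 14 to *d* − 1, so the count is max(0, *s* − (*d* − 14)).

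| AID start | Weeks 1-2 | Weeks 3-4, mean (maximum) | Weeks 5-8 |
|---|---|---|---|
| Day 0 | 0 | 0 (0) | 0 |
| Day 3 | 3 | 0.25 (2) | 0 |
| Day 7 | 7 | 1.75 (6) | 0 |

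For example, with *s* = 7 and block starts on days 15 to 26, the counts are 6, 5, 4, 3, 2, 1 and then zeros: 21/12 = 1.75. If the 14-day footnote applied and AID started on day 14, a block on day 14 would have 14 of 14 pre-AID nights, falling by one per day to 0 on day 28.

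**Scale.** Protocol 1.3 gives pilot time in range rising from 56% to 71% (15 points) and mean glucose falling from 184 to 163 mg/dL (21 mg/dL). These are 24-hour values, and applying them to the night is an assumption.
- Day-7 start, weeks 1-2: 7/14 × 15 = 7.5 points; 7/14 × 21 = 10.5 mg/dL.
- Day-3 start, weeks 1-2: 3/14 × 15 = 3.2 points; 3/14 × 21 = 4.5 mg/dL.
- Day-0 start: 0.

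Median time below 54 mg/dL in the pilot was 0.00% both at baseline and on the system, so that metric would move little.

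**After restricting to nights on or after AID start.** The pre-AID count is 0 for the day-0, day-3 and day-7 starts in every period, and all 14 nights can still be found within 91 days. For weeks 1-2 blocks, the average number of subsequent nights needed is 7.5, 9.5 and 11.5 for starts on days 0, 3 and 7, against 7.5, 6.5 and 4.5 under the present rule.

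**The case against.** The best defense is that the problem is confined to a minority. Protocol 4.6 says the pump and closed loop are generally started on the day of randomization, and such a participant has no pre-AID nights in the pool. That stands and sets the limits of the point.

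A reader might go further and infer from SAP 2, which speaks only of the previous 14 nights, that every week 1-2 challenge is compared with nights from before randomization. The documents do not support this. The first bullets of 5.4 and 5.5 confine the metrics to the 13-week follow-up, 5.3 treats baseline as a separate period, and 8.3 points to 5.4 for the 14 nights. The fallback to subsequent nights points the same way: run-in participants have at least 21 days of CGM before randomization, so an unlimited look-back would rarely need it.

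It can also be argued that nights before pump start are not in the pool at all, because 5.4 uses Tandem pump CGM with Dexcom data only to fill gaps. That is possible but not decisive: 5.3 uses the same wording for follow-up in general while including everything after randomization.

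The scale is open to challenge too. The pilot was a 30-person single-arm study in which 13 used no bolus insulin, and an overnight effect of the same size is not shown. The day-7 example is the maximum delay under the protocol text. Finally, the comparison is within the AID group, outside the hierarchy of SAP 8.2 and in its own false-discovery group in SAP 16.

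**Conclusion.** The point holds for participants with a deferred pump start whose challenges fall in about weeks 1-4, and for those who discontinue AID soon enough after an early challenge that later off-system nights fill the 14. Under the protocol's 7-day limit, up to half of the reference nights are pre-AID, worth about 7.5 points of time in range and 10.5 mg/dL if the pilot effect carries over to the night. The likely direction is to understate a post-challenge rise in glucose. How many participants defer is not stated, so no average over all challenges can be given. The primary endpoint, the hierarchy and all between-group comparisons are untouched. The change is still worth making before analysis, because it removes a bias from the only formal challenge test at almost no cost.

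**What to change.** 1. In SAP 5.4 and 5.5, restrict reference nights to nights on or after AID initiation and before any AID discontinuation. Keep the present order: prior nights first, then subsequent nights.
2. Put no closed-loop-use condition on the challenge night. Protocol 4.6.3 and 4.6.4 have Control-IQ turned off for four hours after insulin by syringe. Four of the eight hours from 10PM to 6AM leaves 50% closed-loop time, so applying, say, the per-protocol 80% threshold would delete nights that went badly. A closed-loop threshold for the reference nights alone can be a sensitivity analysis.
3. Align SAP 2 with 5.4: prior then subsequent nights, and a two-day rather than one-day challenge-free gap.
4. Reconcile the 7-day and 14-day statements on pump start in the protocol and SAP. The filter uses the actual start date and works under either.

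The cost is a few lines of SAP text and one date filter. Early challenges will draw more of their reference nights from later weeks. A participant who stops AID soon after an early challenge may miss the 72-hour minimum (72/8 = 9 full nights) and drop out of the comparison for that session.

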#### 279 5.5 Calculation of CGM Metrics during Scheduled Exercise Challenges

- The exercise challenges will happen and the metrics will be calculated only during the 13 weeks
   of follow-up in the AID group, and are based on either Tandem pump CGM data or Dexcom
   CGM data if obtained to fill any Tandem data gaps.
  - Will be calculated only if the exercise session was recorded on the CRF. The date-times of the challenge-related events, along with other relevant details about the challenge will be recorded on the CRF and will be tabulated.
  - All data between the start of the exercise challenge and 6:00AM next morning will be included.
    - For each exercise, two different periods will be considered, and two separate glycemic metrics will be calculated:
      - During and two hours following the end of the exercise the period between the start and 2 hours following the end of exercise as recorded on CRF, and
      - Overnight following the exercise the period between 2 hours following the end of the exercise and 6:00AM next morning.
- At least 1hr (or 12 CGM readings) are required for each one of the two periods associated with an individual exercise session for the CGM metrics to be calculated.
  - Each CGM reading during an exercise session will be given equal weight.
    - The unit of analysis is an individual exercise session and any participant with at least one exercise challenge completed will be included in these analyses.
- The metrics calculated and reported here will include % time below 54, 70, 70-180, above 180, 250, 300 mg/dL and mean glucose.
- The above glycemic metrics will be calculated during the night following the exercise challenge (10PM to 6AM) and will be compared with the corresponding metrics calculated during 14 nights without any challenge in the previous two days as described above for meal challenges.
   The nights will be pooled together when compared with the night following the exercise challenge. At least 6hr of CGM data are required for the night following the exercise challenge and at least 72hr are required for the previous and pooled 14 nights for these metrics to be calculated and formally compared.
- 307

266

269

270

278

283

284

285 286

287

288

289

290

291

292

295

296

297

#### **308 5.6 Calculation of Insulin Metrics**

- Insulin details (like units and numbers of boluses and basal) over the previous 7 days will be captured on a CRF at randomization, 1, 8, 13 weeks, or at the early termination in both arms. In the AID arm, detailed insulin data will be available from the Tandem pump download.
- CRF data in the Control arm and CRF data (baseline) and Tandem pump data (follow-up) in the AID arm will be used for the calculation of these metrics.
- In the Control group, the CRF data completed at 1 week prior to randomization will serve as baseline; while the CRF data completed at 13 weeks (or at early termination) will serve as the follow-up data.
- In the AID group, Tandem pump data from the week prior to randomization and the week prior to the 13 weeks visit will be used to define and calculate baseline and follow up metrics. If the 13 weeks visit occurs after 91 days from randomization, then the data from days 84 to 90 will be used. If a participant terminates the study earlier than 13 weeks, then the last 7 days in the study will be used to define follow-up.
- For the AID group, will include only days with complete insulin data and at least 5 such days are required for the metrics to be calculated. If there are not 5 such days, the participants will not be included in the insulin analyses. Since Tandem pump automatically generates a basal record every hour, at least 20 such hourly records are required for a day to be considered complete with insulin data and to be counted towards the minimum of 5 days.
  - Weight at baseline and at 13 weeks will be used to calculate insulin units/kg metrics.
- 327 328 329

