162 163 164 165 166	Data downloaded from the CGM, pump, and the home glucose and ketone meter will be collected for the study as measures of diabetes self-management behaviors. Downloaded data from the participant's personal CGM or pump (if any) will include data from prior to the date of the screening visit. Some people may be uncomfortable with the researchers' having such detailed information about their daily diabetes habits.
167	1.5.2 Known Potential Benefits
168 169 170	Participants may experience a significant improvement in glucose control. Hypoglycemia is the number one fear of many individuals taking insulin, and this fear often prevents optimal glycemic control. Hyperglycemia will likely be reduced as well.
171	giyeemic control. Trypergrycemia will likely be reduced as well.
172	In addition, users of insulin pumps often take less insulin than users of basal/bolus injection therapy. This may lead to weight loss, which will be tracked over the course of the study.
172 173 174 175	In addition, users of insulin pumps often take less insulin than users of basal/bolus injection
173 174	In addition, users of insulin pumps often take less insulin than users of basal/bolus injection therapy. This may lead to weight loss, which will be tracked over the course of the study. It is expected that this protocol will yield increased knowledge about using an AID system to control glucose levels in people with type 2 diabetes. The individual participant may or may not

187 188	belief of the investigators that this study also presents prospect of general benefit to others with diabetes.
189	1.6 General Considerations
190 191 192	The study is being conducted in compliance with the policies described in the study policies document, with the ethical principles that have their origin in the Declaration of Helsinki, with the protocol described herein, and with the standards of Good Clinical Practice (GCP).
193 194 195 196	In accordance with 21 CFR 812.66, the protocol is considered a significant risk device study, due to the fact that the closed loop system is investigational in the population under study. Therefore, an investigational device exemption (IDE) from the U.S. Food and Drug Administration (FDA) is required to conduct the study.

Chapter 2: Study Enrollment and Screening

197		Chapter 2: Study Enrollment and Screening	
198		2.1 Participant Recruitment and Enrollment	

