#### 504 8.6. Insulin, Weight, Blood Pressure, and Lipids Analyses

- For insulin, weight, BMI, blood pressure, lipid, and creatinine metrics, summaries and comparisons will
   be made using similar statistics and linear models as described above for the primary HbA1c analysis.
- 507 For insulin metrics, formal analyses will be done comparing the 13-week metrics between the two
- 508 groups while adjusting for baseline. In addition to these, tabulations and plots will be done with insulin
- 509 metrics at baseline, 1, 8, and 13 weeks. Additionally, the post-randomization insulin data in the AID

510 group will be differentiated by manual or automatic mode of delivery – in terms of events and amount of 511 insulin.

512

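### Insulin at 13 weeks is read from a CRF in Control and from the pump download in AID, so any systematic difference between the sources enters the tested treatment difference

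*SAP*

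**What the plan says.** SAP 5.6 has insulin over the previous 7 days "will be captured on a CRF at randomization, 1, 8, 13 weeks, or at the early termination in both arms". It then assigns the sources: "CRF data in the Control arm and CRF data (baseline) and Tandem pump data (follow-up) in the AID arm will be used". For Control the 13-week or early-termination CRF is the follow-up value. For AID it is the pump download for the final week.

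A later item in the same section gives a different AID baseline: "Tandem pump data from the week prior to randomization and the week prior to the 13 weeks visit will be used". That conflicts with the CRF baseline just quoted.

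Three further rules differ by arm:
- **Completeness.** AID needs at least 5 complete days, and "at least 20 such hourly records are required for a day to be considered complete". Anyone short of this is left out of the insulin analyses. No such rule is given for Control.
- **Window.** SAP 5.8 applies the day 61 to 121 window to Control insulin only.
- **Late visits.** In AID, if the visit falls after day 91, days 84 to 90 are used.

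SAP 8.6 makes this a test: "For insulin metrics, formal analyses will be done comparing the 13-week metrics between the two" groups, adjusted for baseline. SAP 5.2 lists total, bolus and basal insulin (units and units/kg) and percentage basal. SAP 16 puts insulin in a group controlled by adaptive Benjamini-Hochberg, and Protocol 11.4.3 classes these endpoints as exploratory.

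**The concern.** At the time point that is tested, every Control value comes from one source and every AID value from another. A systematic difference between sources then looks exactly like a treatment effect. If the AID baseline is the CRF, both arms start on the same source and only AID changes, so the model has nothing with which to separate the change of source from the change of therapy.

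The documents give reasons to expect the sources to differ. Protocol 4.6.3 and 4.6.4 provide for insulin by syringe in some situations, which a pump download would not record. A day with 20 of 24 hourly basal records counts as complete. How the CRF is filled in is not described. No CRF-to-CRF analysis or agreement check is planned, and the sensitivity analyses in SAP 8.4 concern HbA1c.

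What is at stake is any statement about insulin dose under the system. Protocol 1.5.2 notes that "users of insulin pumps often take less insulin than users of basal/bolus injection therapy", so a lower AID figure would readily be accepted as real.

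**Working it through.** **1. The plan's own figure.** The only power statement is for HbA1c (SAP 4): SD 1.0, correlation 0.3, 300 completers, taken as 200 AID and 100 Control from the 2:1 allocation.
- Residual SD = 1.0 × √(1 − 0.3²) = 0.954.
- SE = 0.954 × √(1/100 + 1/200) = 0.117.
- Detectable difference = (1.960 + 1.282) × 0.117 = 0.379 at 90% power. The same formula gives 0.350 at 85% and 0.327 at 80%.

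The stated 0.38, 0.35 and 0.33 reproduce, so the same SE formula is used below.

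**2. What baseline adjustment removes.** Let b be the mean source difference at follow-up and ρ the baseline to follow-up correlation.
- AID baseline from the CRF: bias = b. None is removed.
- AID baseline from a pump: bias = b(1 − ρ). Only ρb is removed.

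A simulation of the adjusted analysis (3000 runs, b = 0.2 SD, no true effect, CRF baseline) returned mean estimates of 0.20 SD at both ρ = 0.5 and ρ = 0.7, with rejection in 46% and 63% of runs. With a pump baseline the estimates were 0.10 and 0.06 SD.

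**3. Illustration in units/day.** The documents give no insulin mean, SD or source difference. Assumed: mean 90 units/day, residual SD 20 to 40, 200 versus 100 analysed, CRF baseline.
- SE = SD × √(1/200 + 1/100) = 2.45 (SD 20) to 4.90 (SD 40).
- Bias = 90 × source difference × share of Control affected.
- P(p<0.05 with no true effect) = Φ(bias/SE − 1.96) + Φ(−bias/SE − 1.96).

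For 10% in all Control, bias = 9 and bias/SE = 1.84 to 3.67. For 10% in a quarter, bias = 2.25 and bias/SE = 0.46 to 0.92.

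| Source difference | All Control | Half | A quarter |
|---|---|---|---|
| 5% | 15-45% | 7-15% | 6-7% |
| 10% | 45-96% | 15-45% | 7-15% |
| 15% | 79-100% | 28-79% | 11-28% |

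The sign of the difference does not change these probabilities. The quarter column takes the recruitment goal of at least 25% injection users (Protocol 2.1) as a low case and assumes no source difference for personal-pump users.

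**4. The same check in SD units.** For ρ from 0.3 to 0.9 and a CRF baseline, rejection is 14-47% at b = 0.1 SD and 40-96% at b = 0.2 SD. With an AID pump baseline it is 5-9% and 7-22%. With b = 0 it is 5.0%.

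All these rates are at unadjusted p<0.05. Under Benjamini-Hochberg the rate also depends on the other p-values in the group and is not computed here.

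**5. Who is dropped.** Protocol 5.5 asks AID participants who stop the system to stay through week 13 and returns them to their pre-study regimen. Having no pump data in the final week, they fail the 5-day rule in SAP 5.6 and leave the insulin analysis. SAP 6.1 says all randomized participants with any data are analysed as assigned. The 13-week CRF would supply their value.

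**The case against.** **Direction.** A reader might infer that the CRF overstates Control insulin, because missed injections stay in, and so the bias favours the device. The documents do not support this. SAP 5.6 and Protocol 5.2.1 both refer to insulin over the last week, which reads as actual use, and forgotten correction doses would reverse the sign. The remark in Protocol 1.5.2 is general, and Control may itself include pump users. The 20-of-24-hour rule does not show undercounting either: up to 4/24 = 16.7% of basal hours may lack a record, but the SAP does not say that they count as zero. This part of the objection stands.

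**Size.** The high rates assume that every Control value is shifted. If only injection users are affected and they are a quarter of Control, even a 15% difference gives 11-28%. The rates also ignore the planned multiplicity rule. This stands, and the figures are illustrations.

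**Remedy.** A reader might conclude that CRF-to-CRF should replace the download as the main comparison. That goes too far. Control-IQ adjusts basal delivery and gives automatic corrections, which nobody can recall over 7 days, and system data are reviewed at each visit. The AID CRF may well be copied from the pump. CRF-to-CRF would then keep the same asymmetry and add transcription error. This stands as a reason to make it an additional analysis.

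None of this removes the confounding of source with arm or the exclusion of AID participants who stopped the pump.

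**Conclusion.** The concern holds as a structural weakness in a secondary, exploratory comparison. The arms use different sources at 13 weeks, the difference is formally tested, and adjustment for a CRF baseline leaves the whole source difference in the estimate. If the AID baseline is meant to come from the pump, part still remains. The study pump starts only at or after randomization, so injection users would have no such baseline.

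Direction and size are unknown. Under the assumptions stated, a 10% source difference gives a false-positive probability at unadjusted p<0.05 of 45-96% if all Control values are affected and 7-15% if a quarter are. These are not estimates for this trial. HbA1c and the CGM hierarchy do not depend on the insulin source. The point is worth a cheap correction because it decides whether a reported dose difference can be interpreted.

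**What to change.** In SAP 5.6 and 8.6:
- Add a prespecified between-arm analysis using the CRF in both arms at baseline and at 13 weeks, including AID participants without 5 complete pump days.
- Record on the CRF whether each insulin value comes from a device download or from participant report.
- Report agreement between pump and CRF in AID at 13 weeks.
- State that a between-arm insulin difference will not be interpreted as a treatment effect unless the same-source analysis agrees.
- Reconcile the two statements on the AID baseline source.

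The pump download can remain for the existing comparison and for the AID description of manual and automatic delivery.

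Cost: SAP wording, one source item on the CRF, and one or two extra tables; the CRF insulin values are already planned in both arms. CRF values are less precise than the download. Where the AID CRF was copied from the pump, the same-source analysis says nothing about the instrument difference, so agreement there is not reassurance. The source item shows how often that happened.
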